5.5.8 Prohibited medication

Use of the treatments displayed in the below table is NOT allowed during the period specified below in Table 5-1.

Medication/therapy	Prohibited period	Action taken
Tapical corticostoroids (TCS)	a) Within 1 week prior to Baseline	a) Delay randomization to achieve 1-week wash out or discontinue subject from trial
Topical controsteroids (TCS) Topical calcineurin inhibitors (TCI) Other topical treatment for AD such as crisaborole, tar etc. Initiation of treatment of AD with prescription moisturizers or moisturizers containing ingredients such as ceramides, lactic acid, urea, α -hydroxy- or fruit acids, vitamins A or D	b) Treatment period c) Follow up period	 b) Discontinue prohibited medication and continue study treatment OR If the subject meets criteria for rescue medication and only after 4 weeks post Baseline, follow instructions in Section 5.5.6** c) Discontinue prohibited medication, unless patient is in the follow up period after early treatment discontinue prohibited
Systemic immunosuppressive treatments* including but not limited to systemic corticosteroids (e.g., i.v., i.m. or oral), cyclosporine, tacrolimus, cyclophosphamide, azathioprine, methotrexate, mycophenolate mofetil, JAK inhibitors, apremilast, biologic therapies (like dupilumab, etanercept, adalimumab, infliximab, omalizumab), chinese traditional medicine	a) Within 4 weeks prior to Baseline for non biologics / within 3 months prior to Baseline for biologic treatments or within 5 half-lives of Baseline, whichever is longer	a) Discontinue subject from trial and rescreen subject after wash- out and if recruitment period is still ongoing

 Table 5-1
 Prohibited medication/therapy

Medication/therapy	Prohibited period	Action taken		
	b) Treatment period	b) Discontinue prohibited medication and continue study treatment unless there is a specific safety risk for the subject, in the opinion of the investigator in which case study treatment must be discontinued		
	c) Follow up period	c) Discontinue prohibited medication		
Oral antihistamines (H1 antihistamines are allowed if the subject is on a stable dose or used short term to, for example, treat allergies)	a) Within 1 week prior to Baseline	a) Delay randomization to achieve 1-week wash out or discontinue subject from trial		

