	b) Treatment period	b) Discontinue the prohibited therapy, and continue study treatment unless there is a specific safety risk for the subject, in the opinion of the investigator in which case study treatment must be discontinued		
	c) Follow up period	c) Discontinue prohibited medication		
Phototherapy or tanning booths Bleach baths	a) 4 weeks prior to Baseline	a) Discontinue subject from study and rescreen subject after wash- out if the recruitment period is still ongoing		
	b) Treatment period	 b) Discontinue prohibited medication/therapy, and continue study treatment 		
	c) Follow up period	c) Discontinue prohibited medication		
Any investigational treatment	a) Within 5 half-lives of Baseline or until the expected pharmacodynamic effect has disappeared, whichever is longer	a) Discontinue subject from trial and rescreen subject after wash- out if the recruitment period is still ongoing		
	b)Treatment period	b) Discontinue subject from study treatment		
	c) Follow up period	c) Discontinue prohibited medication		
Any drug known to prolong QTc interval (See https://crediblemeds.org/ for details as well as protocol supplementary guidance) Drugs known to be hepatotoxic (please see protocol supplementary guidance) [#]	a) Within 5 half-lives of Baseline or until pharmacodynamic effect has disappeared, whichever is longer	 a) Discontinue subject from study and rescreen subject after wash- out if the recruitment period is still ongoing 		
	b) Treatment period	b) Discontinue study treatment		
Medication/therapy	Prohibited period	Action taken		
---	----------------------------------	---	--	--
Strong (Potent) CYP1A2 inhibitors (see protocol supplementary guidance) for all subjects	c) Follow up period	c) Discontinue prohibited medication (unless taken 4 weeks after early treatment discontinuation where it can be		
For subjects that are poor CYP2D6 metabolizers, strong and moderate CYP1A2 inhibitors (see protocol supplementary guidance)		allowed if medically necessary)		
Patients participating in must not	a) Within 2 weeks of Baseline	a) Patient is not eligible for substudy and will not participate		
take	b) Treatment period	b) Discontinue prohibited		
	c) Follow up period	treatment		
		c) Discontinue prohibited medication		

*CS nasal sprays and eye drops are not considered systemic immunosuppressive treatment

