# **Confounding medications**

Any use of rescue medication or prohibited medication will be considerd as confounding therapy, where rescue medications are collected from the rescue therapy CRF and concomitant medications listed below will be considered as prohibited medications.

- 1. All cases of conmeds in the following ATC classes
  - D07 CORTICOSTEROIDS, DERMATOLOGICAL PREPARATIONS
  - R06A ANTIHISTAMINES for systemic use
- 2. Conmeds in the class L04 IMMUNOSUPPRESSANTS that are also PDs with PD identifier COMD3.

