#### Concomitant medication

Concomitant medications are defined as drugs taken at least once between start and end of study treatment (inclusive)

Concomitant treatments will be displayed for:

- the core study treatment period by the relevant treatment group for that period,
- the extension study treatment period by the relevant treatment group for that period

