# 2.5 Analysis of the primary objective

# 2.5.1 Primary endpoint

The primary objective for the extension study is to assess safety of ZPL389. This is described in section 2.8. This section focuses on the primary objective of the core study which is to characterize the dose-response relationship of ZPL389 in subjects with moderate to severe AD assessed by IGA response after 16 weeks of treatment.

The primary clinical question of interest is: What is the effect of ZPL389 versus placebo on IGA response after the full 16 weeks of treatment in patients with moderate or severe atopic dermatitis, who do not use confounding therapy that may affect their AD or the assessment of it, regardless of their use of protocol-allowed concomitant medicatons?

This estimand will enable assessment of the effect of ZPL389 in the absence of confounding medication (such as rescue medication) and after the intended 16 weeks of treatment.

The primary estimand is described by the following attributes:

**Population:** Adult moderate to severe atopic dermatitis patients as defined by the study inclusion and exclusion criteria who were randomized to treatment, and not mis-randomized in the IRT. This implies that analyses will be based on the full analysis set.

**Endpoint:** IGA response at week 16, where IGA response is defined as an IGA score of 0 or 1 with at least a 2 point improvement compared to baseline and no use of confounding therapy before the assessment time point.

**Treatment of interest:** the randomized treatment (ZPL389 or placebo) plus medications as allowed by the protocol but with no further treatment for patients who discontinue study treatment due an AE or lack of efficacy.

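### The SAP's confounding-medication list fails users of permitted H1 antihistamines and misses prohibited AD therapies, contradicting protocol Table 5-1 and the SAP's own estimand

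*SAP*

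**What the plan says.** SAP section 2.1.1, under Confounding medications, treats any rescue or prohibited medication as confounding. Rescue use comes from the rescue CRF. Prohibited medication is whatever appears on a short ATC list: all records in D07 (dermatological corticosteroids), all records in class "R06A ANTIHISTAMINES for systemic use", and L04 immunosuppressants only where the record is also a protocol deviation coded COMD3.

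Protocol section 5.5.8, Table 5-1, lists oral antihistamines as prohibited with an exception: "H1 antihistamines are allowed if the subject is on a stable dose or used short term to, for example, treat allergies". A separate row bars "Any drug known to prolong QTc interval", so some antihistamines remain excluded whatever their dosing pattern. Table 5-1 also prohibits "Other topical treatment for AD such as crisaborole, tar etc", topical calcineurin inhibitors (TCI), "Phototherapy or tanning booths" and bleach baths.

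SAP section 2.5.1 poses the primary question "regardless of their use of protocol-allowed concomitant medicatons" and makes protocol-allowed medication part of the treatment of interest. A responder must have used no confounding therapy before the assessment. Sections 2.6.1 and 2.6.5 carry the rule to EASI50 and EASI75. Section 2.6.2 sets EASI data after confounding use to missing for the main percent-change estimand.

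**The concern.** The list is too wide in one place and too narrow in another.

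A subject who took a short, permitted antihistamine course for an allergy and was clear or almost clear at Week 16 is a non-responder under section 2.1.1. Under section 2.5.1 that medication should have been disregarded. A programmer cannot satisfy both.

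A subject who had phototherapy or used crisaborole has broken Table 5-1 with a treatment aimed at AD, yet nothing on the list catches it. That subject can be a responder.

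The protocol would have settled such cases by blinded adjudication (section 8.5). The SAP drops adjudication, so the list alone now sets responder status for the primary endpoint.

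**Working it through.** **Setting the texts side by side**

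| Therapy | Protocol Table 5-1 | SAP 2.1.1 list |
|---|---|---|
| H1 antihistamine, stable dose or short term, not barred by another row | Allowed | Confounding (all R06A) |
| Antihistamine barred by another row, e.g. QTc | Prohibited | Confounding |
| Crisaborole, tar, other non-steroid topical AD treatment | Prohibited | Not listed |
| TCI outside rescue | Prohibited | Not named |
| Phototherapy, tanning booths, bleach baths | Prohibited | Not listed |

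Three further points follow from the text.

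- *Timing.* The SAP's only definition of concomitant medication (section 2.4.2) takes in any drug used even once while on study treatment. On that reading, a stable antihistamine begun before Day 1 and continued is caught from the start.
- *Omitted users stay in the analysis.* For phototherapy, tanning booths and bleach baths the Table 5-1 action during treatment is "Discontinue prohibited medication/therapy, and continue study treatment". The action for unlisted topical treatments likewise keeps the subject on study drug.
- *Coding.* Procedures and non-drug therapies are coded in MedDRA (protocol 8.3, SAP 2.4.2), so an ATC list cannot reach them.

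**Scale**

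The documents give no usage rates, so the following is illustrative. Inputs from the documents: 187 interim patients (SAP 1.1), allocation 2:1:1:2:2, planning rates of 10% on placebo and at most 20 points more on ZPL389 (protocol 9.8). Assumptions: the 187 split in the allocation ratio, and a share f of would-be responders used permitted antihistamines.

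Arm sizes: 187 × 2/8 = 46.75 and 187 × 1/8 = 23.4.

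Would-be responders:
- planning rates, taking 30% in every active arm: 46.75 × 0.10 + 140.25 × 0.30 = 46.75
- 10% in every arm: 187 × 0.10 = 18.7

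Outcomes changed = responders × f:

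| f | Planning rates | 10% in all arms |
|---|---|---|
| 5% | 2.3 | 0.9 |
| 10% | 4.7 | 1.9 |
| 20% | 9.4 | 3.7 |
| 30% | 14.0 | 5.6 |

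Users already failed through rescue or discontinuation lower these counts.

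Effect on the comparison: each arm's rate becomes p(1 − f). With equal f, the difference is (p_active − p_placebo)(1 − f). A true difference shrinks, and a zero difference stays zero. With unequal f it does not: at p = 10%, f = 20% on placebo and 10% on active, the rates are 10 × 0.80 = 8% and 10 × 0.90 = 9%, a 1-point artefact.

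Omitted therapies: each user wrongly counted as a responder adds 100/46.75 = 2.1 points to a larger arm or 100/23.4 = 4.3 points to a smaller one.

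**What the planned analyses cover**

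Supportive estimands 1 and 2 both set data after any discontinuation to missing and differ in whether confounding use counts as failure. Their gap in each arm roughly bounds the effect of all listed use, rescue included. Supportive estimand 4 avoids the set-to-missing rule for EASI. None isolates permitted antihistamines, and none counts the omitted therapies as failures.

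**The case against.** The strongest defence is that the widening was declared. SAP sections 2.5.1 and 4 say that any confounding use, rather than only adjudicated use, now counts as non-response. Adjudication might itself have judged some permitted antihistamine use confounding. A flat class rule is also simple to apply, whereas the supplied text does not define a stable dose or short-term use, and it shows no deviation code for antihistamines.

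Part of this stands. Counting all antihistamine use is a choice the sponsor could make. But those sections declare only that adjudication was dropped. They do not say that permitted drugs become prohibited or that prohibited AD therapies go uncounted, and the estimand wording still says the opposite. If the broad rule is intended, the text is still wrong.

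Two limits should be kept in view. The documents do not show the contents of the ATC classes, so the TCI gap is a reading of the class titles, supported by the protocol and SAP naming TCI separately from corticosteroids and immunosuppressants. TCI entered on the rescue CRF is caught. And 187 is the interim count. The final number is not given, and the SAP reports no treatment effect at the interim, which makes the 10%-in-all-arms column the more relevant one.

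**Conclusion.** The concern holds and should be fixed. Applied exactly as written, the list produces responder flags that contradict Table 5-1 and the SAP's primary estimand, in both directions. This conclusion rests on the text alone and needs no assumption about usage.

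The size and net direction cannot be determined from the documents. On the stated assumptions, the antihistamine rule changes roughly 1 to 6 outcomes among 187 patients at 10% response in all arms, or 2 to 14 at planning rates. With equal use it cannot create a difference where none exists; with unequal use it can.

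The trial stopped for lack of efficacy, and the SAP reports that the treatment of confounding medication made no difference to its overall conclusions. The stopping conclusion is therefore unlikely to change. What is at stake is the accuracy of the response rates in the study report.

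**What to change.** Before database lock, reconcile the list in SAP 2.1.1 with Table 5-1:

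1. Flag R06A only where the use is not permitted under any Table 5-1 row. A recorded protocol deviation, as already used for L04, is one way to do this if such a code exists.
2. Add the unlisted prohibited AD drugs, including TCI outside the rescue CRF, and flag phototherapy, tanning booths and bleach baths from the MedDRA-coded procedure records.
3. Confirm how systemic corticosteroids are captured; the supplied text does not show it either way.
4. Use this one list wherever confounding therapy is invoked, and record the change in SAP section 4.

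If the sponsor means all R06A use to count, the alternative is to stop calling it prohibited, amend the estimand wording in section 2.5.1, and report a sensitivity analysis that does not count permitted H1 use. The omitted therapies still need adding.

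The cost is SAP wording and a revised flag from data already collected. The downside is a small review of medication, procedure and deviation records. Because it follows an unblinded interim analysis, it should be done blind to treatment by staff who were not unblinded then.

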# 2.2 Analysis sets

Randomized Set (RAN): All subjects randomized. Subjects will be analyzed according to the treatment assigned to at randomization.

Full Analysis Set (FAS): All subjects to whom study treatment has been assigned. Subjects will be analyzed according to the treatment assigned to at randomization. Mis-randomized subjects (mis-randomized in IRT) will be excluded from FAS. Mis-randomized subjects are defined as cases where IRT contacts were made by the site either prematurely or inappropriately prior to confirmation of the subject's final randomization eligibility and no study medication was administered to the subject.

Safety Set: All subjects who received at least one dose of study treatment. Subjects will be analyzed according to treatment received.

Extension study set: All subjects in the full analysis set who have at least one visit in the extension study.

The protocol deviation codes leading to exclusion from the analysis sets defined above are presented in below.

Analysis set	PD codes that cause a subject to be excluded	Non-PD criteria that cause a subject to be excluded
Randomization set	None	Not-randomized.

Table 2-2Subject classification rules

Novartis SAP	For business use only Page CZPL389A2	
Analysis set	PD codes that cause a subject to be excluded	Non-PD criteria that cause a subject to be excluded
Full analysis set	None	Not-randomized, mis- randomized.
Safety set	None	No treatment taken

# 2.3 Patient disposition, demographics and other baseline characteristics

# 2.3.1 Patient disposition

Patient disposition will be summarized based on the randomization set and will focus on showing the number of patients enrolled and the times at which they discontinued the study, including how many progressed to the extension study and how many did not. Data will be summarised by treatment group to determine whether discontinuation rates and reasons were similar across groups.

The key focus is on enrolment and discontinuation during the core study. Subject disposition in the extension is unlikely to be as intended due to the early stopping of the trial.

Since part of the study was conducted during the COVID-19 pandemic summary tables will also indicate how many patients were enrolled and completed the trial during the pandemic time period.

# 2.3.2 Demographics and baseline characteristics

The demography and baseline characteristics summaries are intended to answer the questions:

- Is the trial population the one we intended to recruit?
- Are the characteristics of the trial population similar across treatment groups?

Contrary to the protocol, demographics and baseline characteristics will be summarized for the full analysis set instead of the randomized set. This will enable a comparison of the population for whom efficacy data is presented, with other studies.

Only key demographic and baseline characteristics that would be important to understand the patient population and put efficacy results into context of other trials will be presented.

Specifically these are:

- Age and age category (<65 years, 65 years and older)
- Weight
- Body mass index
- Gender
- Race
- Smoking status
- Baseline IGA score categories (moderate, severe)
- Baseline EASI

- Baseline total body surface area (BSA) affected by AD
- Time since diagnosis of AD
- Age at the time of diagnosis of AD
- Previous exposure to systemic corticosteroids(yes, no)
- Previous exposure to topical corticosteroids (TCS) therapy (yes, no)
- Previous exposure to topical calcineurin inhibitors (TCI) therapy (yes, no)
- Previous exposure immunosuppressant therapy for atopic dermatitis (yes, no)
- Previous exposure biologic systemic therapy for atopic dermatitis (yes, no)
- Previous exposure to other therapy for atopic dermatitis (including phototherapy and tanning booths) (yes, no)

# 2.4 Treatments (study treatment, rescue medication, concomitant therapies, compliance)

## 2.4.1 Study treatment / compliance

The summaries of study treatment intake are intended to answer the question:

• Was there a difference in study treatment intake across the dose groups?

Other questions related to the intake of study treatment, such as whether this affected the efficacy outcomes are considered in later sections.

This summary will be based on the safety set to include all patients who received study treatment according to the treatment they received.

Although not expected based on the interim results, in case there are large differences between study analysis sets, further summaries may be produced based on other analysis sets.

Duration of exposure is defined as the time from first dose of study medication to the last dose, i.e.

- duration of exposure (days) = last dose date first dose date +1
- duration of exposure (years) = duration of exposure (days) / 365.25

In addition to summaries of the total duration of exposure, the number of subjects with exposure of particular durations will be summarized, i.e. the number and percentage of patients with exposure of

- $\geq 2$  weeks
- $\geq 4$  weeks
- $\geq 8$  weeks
- $\geq 12$  weeks
- $\geq 16$  weeks
- $\geq 20$  weeks
- $\geq 24$  weeks
- $\geq 28$  weeks

- $\geq 32$  weeks
- $\geq 40$  weeks
- $\geq$ 44 weeks
- $\geq 1$  year
- >56 weeks
- ≥1.5v
- ≥2y

#### 2.4.2 **Prior**, concomitant and post therapies

The summaries of study treatment intake are intended to answer the question:

- What medications were used by patients before start of this trial?
- What medications were used by patients whilst on treatment in this trial?
- What medications were used by patients after study treatment in this trial

Other questions related to the intake of confounding treatment (treatment that may be considered to affect the efficacy outcomes) are considered in later sections.

This summary will be based on the safety set to include all patients who received study treatment according to the treatment they received.

Medications will be presented by ATC code and preferred term. ATC codes will be displayed in alphabetical order, and grouped by anatomical main group (the first level of the ATC code).

Medical procedures and significant non-drug therapies as coded in MedDRA will be summarized along with medications.

#### Prior medications

Prior medications are defined as drugs taken and stopped prior to the first dose of study treatment in the core study.

These will be displayed for the baseline period by core study treatment group

#### Concomitant medication

Concomitant medications are defined as drugs taken at least once between start and end of study treatment (inclusive)

Concomitant treatments will be displayed for:

- the core study treatment period by the relevant treatment group for that period,
- the extension study treatment period by the relevant treatment group for that period

#### Follow-up medications

Follow-up medications are defined as drugs started after the last dose of study treatment.

These will be displayed for the follow-up period by the last treatment received prior to entering the follow-up period.

# 2.5 Analysis of the primary objective

# 2.5.1 Primary endpoint

The primary objective for the extension study is to assess safety of ZPL389. This is described in section 2.8. This section focuses on the primary objective of the core study which is to characterize the dose-response relationship of ZPL389 in subjects with moderate to severe AD assessed by IGA response after 16 weeks of treatment.

The primary clinical question of interest is: What is the effect of ZPL389 versus placebo on IGA response after the full 16 weeks of treatment in patients with moderate or severe atopic dermatitis, who do not use confounding therapy that may affect their AD or the assessment of it, regardless of their use of protocol-allowed concomitant medicatons?

This estimand will enable assessment of the effect of ZPL389 in the absence of confounding medication (such as rescue medication) and after the intended 16 weeks of treatment.

The primary estimand is described by the following attributes:

**Population:** Adult moderate to severe atopic dermatitis patients as defined by the study inclusion and exclusion criteria who were randomized to treatment, and not mis-randomized in the IRT. This implies that analyses will be based on the full analysis set.

**Endpoint:** IGA response at week 16, where IGA response is defined as an IGA score of 0 or 1 with at least a 2 point improvement compared to baseline and no use of confounding therapy before the assessment time point.

**Treatment of interest:** the randomized treatment (ZPL389 or placebo) plus medications as allowed by the protocol but with no further treatment for patients who discontinue study treatment due an AE or lack of efficacy.

